## **Ethical Assurance for Protection of Human Rights**

Describe in the space provided the justifications for conducting this research in human subjects. If the study needs observations on sick individuals, provide sufficient reasons for using them. Indicate how subject's rights are protected and if there is any benefit or risk to each subject of the study.

Signed consent will be obtained from parents for participation of the children in the study for vaccination and specimen collection (Appendix I and II). All data related to side-effects of each dose of the vaccine will be examined by a safety monitoring committee. The reaction surveillance will be carried out for 3 days after each dose of the vaccine and recorded systematically (Appendix-IV).

#### Use of Animals

Describe in the space provided the type and species of animal that will be used in the study. Justify with reasons the use of particular animal species in the experiment and the compliance of the animal ethical guidelines for conducting the proposed procedures.

Not needed for the study.

# Dissemination and Use of Findings

Describe explicitly the plans for disseminating the accomplished results. Describe what type of publication is anticipated: working papers, internal (institutional) publication, international publications, international conferences and agencies, workshops etc. Mention if the project is linked to the Government of Bangladesh through a training programme.

The information obtained from this study will help in the field-testing of the ETEC vaccine and future evaluation of its protective efficacy.

| Principal Investigator: Last, | first, middle |  |  |
|-------------------------------|---------------|--|--|
|                               |               |  |  |

# **Collaborative Arrangements**

Describe briefly if this study involves any scientific, administrative, fiscal, or programmatic arrangements with other national or international organizations or individuals. Indicate the nature and extent of collaboration and include a letter of agreement between the applicant or his/her organization and the collaborating organization. (DO NOT EXCEED ONE PAGE)

This is a collaborative study between the International Centre for Diarrhoeal Disease Research, Bangladesh (ICDDR,B), the Department of Medical Microbiology and Immunology, Goteborg University, Goteborg, Sweden and the Johns Hopkins University, Baltimore, MD, USA.

#### TIME FRAME (two years)

- a) Enrollment of children, administration of vaccine and laboratory assays (ASC response to vaccine antigens, stimulation of MNC for cytokine assays) first 9 months.
- b) Completion of laboratory assays (vaccine-specific ELISA for plasma and faecal samples and cytokine assays)- next 12 months.
- c) Evaluation of results and report writing. Plan and initiate study to progress to children from 3 months to 3 years for protective efficacy studies.

#### Response to comments of reviewers

#### Reviewer 1

- 1. As suggested, children with ongoing antibiotic treatment will not be enrolled in the study. Only children who have not have any antibiotic over the last seven days will be selected
- 2. We have recently carried out a study to determine the prevalence of ETEC diarrhoea in the 2% surveillance of diarrhoeal patients at ICDDR,B and found that the incidence increases from 3 months onwards. It is possible that the vaccine can be given at one of the EPI schedules, probably with the dose given at 41/2 months. This has to be considered when a large protective efficacy trial is conducted.
- 3. Studies in Egypt and phase I studies in Bangladesh in adults and children have shown that a 3 day follow-up after vaccination is sufficient. Since the ETEC vaccine is a killed vaccine it is sufficient to observe reactogenicity for 3 days only.
- 4. As a benefit, all children in the study will be under supervision of a trained physician during the entire period of the study. In case of illness, medication will be given as and when necessary. Since this is a double blind study the same benefit has to be given to both the groups. All the children irrespective of their groups, will be given a month's supply of multivitamin supplement at the end of the study.

#### Reviewer 2

- 1. A primary safety endpoint has now been defined as was suggested (page 9).
- 2. The sample size has been increased after taking into consideration the prevalence of ETEC in children in Bangladesh (Page 9).
- 3. The IgA specific ASC response will only be studied to only a few of the vaccine antigen. Since a two colour ELISPOT procedure will be used this will require much less numbers of mononuclear cells. In the younger children only the serum and the fecal samples will be used for antibody assays and the cytokine assays. These have been clarified in the methods section (Page 10).
- 4. Data analyses section has been written in more detail now.
- 5. The completeness of dosing will be monitored. Those ingesting at least 90% of the vaccine will be studied further. Provision has been made in the case report (Appendix V) to monitor the intake of the dose.
- 6. The results from the children will be analyzed separately and together from information obtained from both groups.
- 7. The same buffer will be used for the two groups in the study and has been clarified.
- 8. Diarrhoea has been defined in the protocol (page 9) and the reaction form (appendix V) modified as well.
- 9. Results from children taking only one dose of the vaccine will also be used for data analysis. Those children who are not able to take a second dose of the vaccine due to fever or diarrhoea will be excluded from the study and not be given a dose later.
- 10. A positive response will be defined in terms of a two fold increase over the individuals baseline value. Only ASC levels > 10 ASCs per 10^7 MNCs in the post immunization specimen will be considered a responder.

| cipal Investigator: Last, first, middle |
|---|
|---|

#### **ABSTRACT SUMMARY**

Acute diarrhoeal diseases are a major health problem in developing countries. Infection with ETEC is one of the most common causes of diarrhoea among children in developing countries and it also contributes to malnutrition. The prevalence of toxin types and colonization factors (CFs) of enterotoxigenic *Escherichia coli* (ETEC) was recently studied in fresh samples (n=4662) obtained from a 2% routine surveillance of diarrheal stools for two years from September 1996 to August 1998. It was observed that the prevalence of ETEC was 14% with over 70% isolated in children 0-5 years age range, of whom 93% were in the 0-3 years age range (Qadri et al. 1999). The infection could by prevented by a safe and immunogenic vaccine that is protective in children. One such vaccine undergoing evaluation is the oral inactivated ETEC vaccine consisting of recombinant cholera toxin B subunit (BS) and a mixture of formalin- inactivated whole cell ETEC bacteria expressing colonization factors (BS-CFA ETEC vaccine). The vaccine has been tested in a number of countries in phase-I safety and immunogenicity trails in adults ([name] et al., 1997). These initial vaccine trials have been extended in Egypt to larger field based phase II and phase III studies. It has been tested in adults as well as in children in the 2-12 years old age group (Savarino et al. 1998, 1999) and is now being tested in 6-18 months old children (WHO, 1999). A phase I study carried out in Bangladeshi children in the 3-10 year range has shown that the vaccine is safe and immunogenic (Qadri et al., manuscript submitted). A phase-II safety and immunogenicity study now needs to be carried out in Bangladesh in children who are most at risk to the consequences of ETEC diarrhea i.e. children from 6 months to 3 years of age. Based on the results of this study, the vaccine can subsequently be extended to a large phase III, protective efficacy trial.

#### Clarification of points as required in the attached list are as follows:

- 1. Only children in the 6 month to 3 year age range will be included since ETEC diarrhoea is a major cause of morbidity and mortality in this age and a vaccine is needed urgently for them. Only children whose guardians or parents have given voluntary consent to participate in this study will be enrolled.
- 2. Methods used have very little chance of physical risk.
- 3. Since only blood will be collected there is little risk other than a minimum discomfort at puncture site. After feeding the oral ETEC vaccine the child will be kept under observation for 30 minutes and will also be monitored for side-effects for 3 consecutive days.
- 4. The interview records will be kept in a locker under supervision. Only the investigators will have access to it.
- 5. Informed consent will be obtained from the guardian or parent of the child. The potential risks and the procedures to be carried out are mentioned in the consent form.
- 6. The interview will be conducted in the homes of the children for obtaining history prior to enrollment. Monitoring the side-effects will also be carried out in subsequent home visits. Approximately 30 minutes to 1 hour will be required for the interview.
- 7. The vaccine trial will benefit children in any ETEC endemic country if the trial shows that the vaccine is safe and immunogenic. This will lead to future studies for effectiveness.

| Principal Investigator: Last, first, middle  8. The activity will require collection of stool an children that will be enrolled in the study.   | d small amount of blood from about a third of the total  |
|---|--|
#### Appendix III

# INTERNATIONAL CENTRE FOR DIARRHOEAL DISEASE RESEARCH BANGLADESH, (ICDDR,B)

#### **Study Subject Selection Form**

Safety and immunogenicity study of the oral BS-CFA ETEC vaccination in Bangladeshi children

|                  | Name of the examiner                  |               |           |       |      |  |
|------------------|---------------------------------------|---------------|-----------|-------|------|--|
|                  |                                       | Date of       | interview | 00 00 |      |  |
| 1 D-             | aia daka                              |               |           | DD MM | 1 YY |  |
| 1. Ba            | sic data                              |               |           |       |      |  |
| 1.1. Fa          | mily No.                              |               |           |       |      |  |
| 1.2 Sc           | reening No.                           |               |           |       |      |  |
| 1.3 Str          | Study child's name                    |               |           |       |      |  |
| 1.4 St           | .4 Study child's ID                   |               |           |       |      |  |
| 1.5 Re           | 5 Respondent                          |               |           |       |      |  |
| 1                | l = Mother 2= Fa                      | ther 3= Other |           |       |      |  |
| 1.6 Se           | x                                     | 1 Male        | 2 Female  |       |      |  |
| 1.7 Ag           | ge in months                          |               |           |       |      |  |
| 1.8 Date (Englis | of birth
sh calendar)              | DD MM YY      |           |       |      |  |
| (— 3 -    | · · · · · · · · · · · · · · · · · · · |               |           |       |      |  |
| 1.9 Date o       | of birth                              | 00 00 00      |           |       |      |  |
| (Benga           | di calendar)                          | DD MM YY      |           |       |      |  |

If day is unknown write 15. Month and year must be written. You can write according to Bengali calender at the time of interview, and then translate into English later.]

| Princip | at investigator: Last, first, middle |         |           |            |              |
|---------|--------------------------------------|---------|-----------|------------|--------------|
| -1.10   | Height (cm)                          | 000.0   |           |            |              |
| 1.11    | Weight (kg)                          | 00.0    |           |            |              |
| 1.12    | % of NCHS (W/A)                      | 000.0   |           |            |              |
| 1.13    | % of NCHS (W/H)                      | 000.0   |           |            |              |
| 1.14    | Oedema (Present)                     | 1 = Yes | 2=No      |            |              |
| 1.15    | Presence of illness                  | 1=No    | 2=Fever   | 3= Diarrho | oea 4=others |
| 1.16    | Previous immunization                |         |           |            |              |
| 1.16.1  | DPT                                  | 1=No    | 2= 1 dose | 3=2 dose   | 4= 3 dose    |
| 1.16.   | 2 OPV                                | 1=No    | 2= 1 dose | 3=2 dose   | 4= 3 dose    |
| 1.16.3  | Measles                              | 1=No    | 2= Yes    |            |              |
| 1.16.4  | BCG                                  | 1=No    | 2= Yes    |            |              |

| Princip | al Investig | gator: Last, | first, | middle |  |  |
|---------|-------------|--------------|--------|--------|--|--|
|         |             |              |        |        |  |  |

# Appendix IV

# INTERNATIONAL CENTRE FOR DIARRHOEAL DISEASE RESEARCH BANGLADESH, (ICDDR,B)

Safety and immunogenicity study of the oral BS-CFA ETEC vaccination in Bangladeshi children

# History form of enrolled study subjects

| Vacci  | ne lot No                   | Name of the | examiner  |             |
|--------|-----------------------------|-------------|-----------|-------------|
| 1.     | Basic data                  |             |           |             |
| 1.1.   | Family No.                  |             |           |             |
| 1.2    | Screening No.               |             |           |             |
| 1.3    | Study child's name          |             |           |             |
| 1.4    | Study child's ID            |             |           |             |
| 1.5    | Date of vaccination DD      | MM YY       |           |             |
| 1.6    | Vaccination                 |             | Primary=1 | Secondary=2 |
| 2.0    | Presence of illness         | Yes 2=No    |           |             |
| If yes | 1-                          | res 2INO    |           |             |
| 2.1    | Chief Complain:             |             |           |             |
|        |                             |             |           |             |
| 2.2    | History of present illness: |             |           |             |

| Principal Investigator: Last, first, middle | e |
|---|---|
| •   |   |
|   |   |

#### 2.3 **Physical Examination**

#### 2.3.1 General Examination

Pulse (rate/min)

Heart rate/min

Respiratory rate/min

Temperature (°C)

Anaemia:

1=No 2=mild 3=moderate 4=severe

Clubbing: Jaundice: 1= No 2=Yes

1= No 2=Yes

Cyanosis:

1 = No 2 = Yes

Dehydration: 1= No 2=Some 3= Severe

Skin Condition: 1= Scabies 2=Eczema 3= Others

#### 2.3.2 Systemic Examination

#### 2.3.2.1 Alimentary System

Abdominal distension: 1=No 2=Moderate 3=Severe

Abdominal tenderness: 1=No 2=Yes if tender 3= localized 4= generalized

Liver palpable: 1=No 2=Yes Spleen palpable: 1=No 2=Yes

#### 2.3.2.2 Respiratory System:

Lungs(auscultation): 1=Clear 2=Added sound; if added sound 3=Ronchi 4=Rales

#### 2.3.2.3 Cardiovascular System:

Heart(auscultation): 1=Normal 2=Added sound

#### 2.3.2.4 Nervous System:

Appearance: 1=Normal 2=Irritable 3=Lethargic

#### 2.3.2.5 Locomotor System:

Movement 1=Normal 2=Restricted

#### Appendix V

# Adverse event form Surveillance after Primary vaccination Day 1

1.0 Completeness of dosing. Amount ingested: 1=100% 2=290% 3=<90%

#### 2.0 LOCAL REACTION

| Parameters               |                                   |
|--------------------------|-----------------------------------|
| Abdominal pain           | 1= No 2=Mild 3= moderate 4=severe |
| Cramp                    | 1= No 2= Yes                      |
| Distension               | 1=No 2= moderate 3= severe        |
| Vomiting                 | 1=No 2= Yes                       |
|                          |                                   |
| If yes, number/day       |                                   |
| Other symptoms           | 1=No 2= Yes                       |
| *Diarrhoea [watery stool |                                   |
| or loose stool ]         |                                   |
| If yes above number/day  |                                   |
| (>3)                     |                                   |

\*Diarrhoea defined as passing of ≥ 3 loose or liquid stools per day

#### 3.0 SYSTEMIC REACTION

| Parameters               |              |
|--------------------------|--------------|
| Fever (oral or rectal    | 1= No 2= Yes |
| temp>37.8°C              |              |
| If yes, temperature (°C) |              |
| Loss of appetite/ Poor   | 1= No 2= Yes |
| feeding                  |              |
| Irritability             | 1= No 2= Yes |
| Nausea                   | 1= No 2= Yes |
| Dizziness                | 1= No 2= Yes |
| Exanthema                | 1= No 2= Yes |
| Other                    | 1= No 2= Yes |

#### 4.0 Relation to vaccine

1= None 2= Possible 3= Probable 4= Highly probable

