#### Burden of disease due to ETEC diarrhoea

It has been estimated that ETEC infections alone cause approximately 210 million episodes of diarrhoea and over 380,000 deaths annually in children under 5 years of age (WHO, 1996, 1999). The peak of incidence of ETEC diarrhoea in endemic countries occurs in the first year of life, with a declining incidence with age thereafter. Of the 7-8 episodes of diarrhoea annually in children, in the developing world, at least 2-4 attacks may be due to ETEC (Black, 1993). As a result, ETEC diarrhoea may contribute to growth retardation and death in these children. In addition, it is responsible for over 50% of diarrhoea in travellers to ETEC endemic regions of the world. A high proportion of diarrhoeal illness in military personnel is also caused by ETEC (Wolf *et al.*, 1997). The clinical symptoms of the disease are watery diarrhoea often accompanied by abdominal cramps, malaise and low grade fever. It may last 3-7 days and the disease spectrum can range from mild diarrhoea to dehydrating cholera-like symptoms, which is seen in about 5% of cases (Black, 1986).

The pathogenicity of ETEC is due to their ability to colonize the small intestine and to produce one or both of two types of toxins, the heat stable enterotoxin (ST) (Field et al., 1978) and/or the heat labile enterotoxin (LT)

| $\mathbf{p}_1$ | rincinal | Investigator: | Lact  | first | middle |
|----------------|----------|---------------|-------|-------|--------|
| 1              | шуграг   | mivesugator.  | Last. | HESL  | magae  |

([name] and Holmgren, 1978). These bacteria also possess a variety of surface located adhesins that anchor them to the intestinal mucosal receptors (Gaastra and de Graaf, 1982; Evans and Evans, 1998). This anchorage enables the bacteria to resist the flushing action of the intestinal peristalsis and the toxins are delivered close to the enterocytes. The adhesins are termed colonization factors (CFs) and may be fimbrial, fibrillar or non-fimbrial in structure. Some 20 adhesins have been identified on human ETEC strains (Gaastra and [name], 1996). Of these structures, CFA/I consists of a single subunit, whereas CFA/II may consist of three antigenically separate CS antigens, CS1, CS2 and CS3 (Smyth, 1982). Likewise, it has been found that CFA/IV may consist of CS4, CS5 and CS6 (Thomas et al., 1985).

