#### Safety Monitoring of the Vaccine

On each study day (Days 0,7,14 and 21) clinical history and physical examination will be carried out (Appendix IV). The safety and reactogenicity of the vaccine will be monitored in the subjects by observing for 30 minutes after each dose for occurrence of immediate adverse experiences. On 3 consecutive days after each dose parents will be interviewed for 24 hour recall of symptoms by the health workers and the physician by home visits each day. All side-effects will be recorded in reaction surveillance forms for local and systemic reactions (Appendix V). Reported symptoms will be graded as mild, moderate and severe. In case of serious adverse effects the data will be entered in a separate form (Appendix V). The study subject will be hospitalized at the CRSC of ICDDR,B under supervision of the clinician monitoring the safety of the vaccine. Sample collection

Stool: Stool will be collected prior to vaccination (3 days prior to initial immunization) and subsequently at follow-up visits 7 days after intake of the first as well as 7 days after intake of the second dose of the vaccine. Routine examination of stools will be carried out to detect parasites. Bacteriological examination will be carried out to exclude the presence of enteric pathogens (WHO, 1987). Five lactose-fermenting colonies will be tested for colonization factor expression by dot blot immunoassay techniques and for the enterotoxins LT and ST. Stools will be also be tested prior to intake of the second dose and tested similarly. The stools will also be tested to exclude the presence of ETEC by assaying for LT and ST using the GM1-ELISA technique ([name] and Holmgren, 1978; [name] et al., 1986). Stools will also be collected for preparing faecal extracts for antibody and cytokine assays. Faecal extracts will be prepared (Qadri et al., 1997) and stored at -70°C until tested.

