#### 6.0 Outcome

1= resolved 2= improved 3= unchanged 4= worse

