#### 3.0 SYSTEMIC REACTION

| Parameters   |              |
|--|--------------|
| Fever (oral or rectal temp>37.8°C If yes, temperature (°C) | 1= No 2= Yes |
| Loss of appetite/ Poor feeding                             | 1= No 2= Yes |
| Irritability   | 1= No 2= Yes |
| Nausea   | 1= No 2= Yes |
| Dizziness  | 1= No 2= Yes |
| Exanthema  | 1= No 2= Yes |
| Other  | 1= No 2= Yes |

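### The Appendix V daily sheets print no field to name or grade an unlisted systemic reaction, and one relation, therapy and outcome code serves every symptom on a sheet

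*Protocol*

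**What the plan says.** The section Safety Monitoring of the Vaccine names the instrument: "All side-effects will be recorded in reaction surveillance forms for local and systemic reactions (Appendix V"). It adds that reported symptoms are graded mild, moderate or severe. On serious events it says "In case of serious adverse effects the data will be entered in a separate form (Appendix V").

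Appendix V has six sheets: Days 1, 2 and 3 after each of two doses. Each has a local and a systemic reaction table.

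- The systemic table ends with "Other | 1= No 2= Yes" on all six sheets, and no further row follows.
- Some listed symptoms do have a detail row: "If yes, number/day" after vomiting, a similar row after diarrhoea, and "If yes, temperature (°C") after fever.
- Item 4.0, Relation to vaccine, stands once after both tables: "1= None 2= Possible 3= Probable 4= Highly probable".
- Items 5.0 (therapy required, No or Yes) and 6.0 (outcome, "1= resolved 2= improved 3= unchanged 4= worse") also stand once.

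The Data Analysis section compares individual symptoms between arms by Fisher's exact test. The ethics section says that a safety monitoring committee examines all side-effect data from each dose.

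**The concern.** Safety in children from 6 months of age is the first specific aim, and a larger trial reaching down to 3 months is meant to follow. Such a trial should be able to describe reactions that nobody listed beforehand. On these sheets, different unlisted systemic events fall into one anonymous Other category, so an arm difference in one of them is mixed with unrelated events. This also falls short of the protocol's own statement that all side-effects are recorded and reported symptoms graded.

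The second problem is attribution. Take a child who vomits after the dose and has fever from an unrelated illness on the same day. That child receives one relation code and one outcome code, and no single code need be true of both symptoms. A statistical analysis plan cannot repair this, because the name, grade and symptom-level code were never collected.

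**Working it through.** The point turns on form structure, and the only arithmetic is counting.

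**1. Rows per sheet (Appendix V, items 2.0 and 3.0).**
- Local, named: abdominal pain, cramp, distension, vomiting, diarrhoea = 5.
- Systemic, named: fever, poor feeding, irritability, nausea, dizziness, exanthema = 6.
- Unnamed: *Other symptoms* (local) and *Other* (systemic) = 2.
- Total: 5 + 6 + 2 = 13. It is 12 if the local *Other symptoms* line is only a heading for the diarrhoea row, which the broken table leaves open.

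**2. Codes per sheet (items 4.0 to 6.0).** One relation, one therapy and one outcome code. Over six sheets, a child has 6 × 13 = 78 symptom entries (72 on the lower count) against 6 codes of each kind.

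**3. When the single code fails.**
- One symptom marked: the codes belong to it.
- Several symptoms that share cause, treatment and course: one code fits all. Relation None or therapy No covers the whole sheet.
- Several symptoms that differ in any of these: the code cannot be assigned to a symptom.

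Only the third case loses information.

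**4. Other places where an unlisted event might be named.**
- Appendix IV has free text for the chief complaint and present illness. Safety Monitoring schedules it on Days 0, 7, 14 and 21, outside the three-day recall. It carries no relation, therapy or outcome code.
- The ethics section cites Appendix IV, not Appendix V, for the three-day surveillance. Even on that reading, the form asks about illness present at the time and has no codes.
- The serious-event form would not name a non-serious reaction.

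**5. How many sheets.** With 158 children in each of two age groups, as the sample size section states, the ceiling is 316 × 6 = 1,896 sheets. If 158 is read as the total, which the selection section allows, it is 158 × 6 = 948. Both count every sheet, including symptom-free ones. For scale only: the Background section reports adverse events in about 2–6% of recipients in earlier studies, and 0.02 × 316 ≈ 6 to 0.06 × 316 ≈ 19 children. These rates come from other populations and leave out background illness in this one. They also count children with any event, not sheets with an unlisted event or with differing symptoms.

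**The case against.** **The form was read from PDF and is visibly damaged.** Outcome codes are printed on only two of the six sheets in the text at hand, and a blank line for handwriting beside Other would leave no trace. This is why the point is confined to what is printed. Printed detail rows survive for fever, vomiting and diarrhoea, and none appears for the systemic Other row on any of six sheets. For the local *Other symptoms* row the objection stands, so the fix there is conditional.

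**Other records exist.** Appendix IV has free text and an examination, a physician takes part in the daily home visits, and the Data management section allows extra visits to complete entries. This stands in part: a reader might infer that no unlisted event could ever be identified, and the documents do not support that. But none of these provisions asks for the name of a transient Day 1–3 event or ties a relation or outcome code to a symptom.

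**No planned comparison uses these codes.** This stands. The primary endpoint is diarrhoea, vomiting or cramps, counted regardless of relation, and each listed symptom has its own row.

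**Many symptoms per sheet may not be usual.** A reader might infer from the account of natural disease, "watery diarrhoea often accompanied by abdominal cramps, malaise and low grade fever", that several symptoms per sheet are to be expected. That passage describes ETEC illness, not reactions in healthy, ETEC-negative children given an inactivated vaccine. The Background section's list of reactions in earlier studies (nausea, mild cramps, loose stools) is nearer, but it does not say how often they occurred together.

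**Conclusion.** The point holds as a cheap improvement. Followed as printed, the sheets lose the name and grade of a non-serious unlisted systemic reaction, and they merge relation, therapy and outcome across symptoms that may differ. Appendix IV and the serious-event form fill the gap only in part.

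The size cannot be derived from the documents. A reader might take 1,896 as the number of affected sheets, or conclude that every sheet with two or more symptoms is uninterpretable. Neither follows: the first is a ceiling that includes symptom-free sheets, and codes are lost only where symptoms on a sheet differ in cause, treatment or course. The primary safety endpoint and the listed-symptom comparisons by arm stand. What suffers is the description of unforeseen, related and unresolved events.

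The conclusion assumes that the printed sheets are complete apart from reading damage, and that the serious-event form, which is not seen in the pages available, is used for serious events only.

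**What to change.** On all six Appendix V sheets:

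1. Add an if-yes-specify field and a mild, moderate or severe grade to the systemic Other row. Do the same for the local *Other symptoms* row if it is a separate item.
2. Replace the single items 4.0 to 6.0 with relation, therapy and outcome columns beside each symptom, completed only when that symptom is marked Yes.
3. In the Data Analysis section, add a table of named unlisted events by arm after each dose, beside the listed symptoms.

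The cost is a change of form layout and slightly longer completion for children with symptoms. Sheets for symptom-free children take no longer. The change should be made before enrolment, because names and symptom-level codes cannot be reliably recovered later.
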